### **BIOMARKERS**

---

Assessment of biomarkers in plasma by multiplexed array will be performed. Serum bone biomarkers will also be assessed. In addition, circulating tumor cells (CTCs) may be analyzed in blood samples collected at selected sites. Samples for these assessments will be collected according to the schedule in Appendix A.

In addition, tumor tissue (archival or recently biopsied) will be obtained at enrollment whenever available for exploratory analysis of MET and potentially other pathway components or modulators associated with the mechanism of action of cabozantinib, as predictive biomarkers.

Collection of these samples may be halted early or sampling frequency may be reduced at the discretion of the Sponsor. If the study transitions to the Open-Label Phase or to the Maintenance Phase, biomarkers will no longer be collected.

## HEALTH-RELATED QUALITY OF LIFE (HRQOL)

---

Subjects will be requested to complete the EQ-5D-5L assessment at baseline (Week 1 Day 1; day of first dose) and every 4 weeks through Week 25, then every 8 weeks until the later of 8 weeks after radiographic progression per RECIST 1.1 as determined by the investigator or the date of the decision to permanently discontinue study treatment (Appendix A). Assessments will continue on this schedule irrespective of whether study treatment is given, reduced, interrupted, or discontinued.

If the study transitions to the Open-Label Phase or to the Maintenance Phase, HRQOL assessments will no longer be collected.

## STATISTICAL METHODS

---

The primary efficacy analysis in this study is the comparison of overall survival (OS) in subjects treated with cabozantinib versus placebo.

For the primary endpoint, OS is defined as the time from randomization to death due to any cause. The final analysis of OS is event-driven and will be conducted after at least 621 deaths have been observed.

Progression-free survival (PFS) and objective response rate (ORR) are the secondary endpoints. PFS is defined as the time from randomization to the earlier of either disease progression per RECIST 1.1 as determined by the investigator or death from any cause. ORR is defined as the proportion of subjects experiencing a confirmed complete response (CR) or confirmed partial response (PR) per RECIST 1.1. Inflation of Type I error associated with testing multiple endpoints will be controlled by employing a fixed-sequence testing procedure and a modified Bonferroni procedure (dividing the alpha between the secondary endpoints: 0.04 for PFS, and 0.01 for ORR). The testing of the secondary endpoints (PFS and ORR) will occur only if the result of either an interim analysis or the final analysis of OS achieves statistical significance.

Up to three event-driven analyses of OS are planned: two interim analyses and a final analysis when 311, 466 and 621 deaths (ie, 50%, 75% and 100% information) have been observed respectively. Inflation of Type I error associated with interim analyses will be controlled using a Lan-DeMets O'Brien-Fleming alpha-spending function. Interim analysis of PFS and ORR are not planned.

OS and PFS will be summarized descriptively using the Kaplan-Meier method. Inferential comparisons between treatment arms will use the stratified log-rank test. The hazard ratio (HR) will be estimated using a stratified Cox proportional hazards model. Stratification will be based on the stratification factors used for the randomization. The ORR and 95% confidence intervals (CIs) will be provided. Inferential comparisons between treatment arms will use the Fisher's exact test.

For OS, a total of 621 deaths planned with two interim analyses (at 50% and 75% information) and a final analysis provides the study with 90% power for a 2-sided log-rank test with a 5% level of significance to detect a 31.6% increase in OS (HR = 0.76). Assuming an 8.2 month median OS in the placebo arm and exponential distribution of

OS, this corresponds with an increase in median OS to 10.8 months in the cabozantinib arm. In the current design, the minimum observed effect that would result in statistical significance for OS at the two interim and final analyses are 42.1% improvement (HR = 0.70) from 8.2 to 11.7 months, 25.7% improvement (HR = 0.80) from 8.2 to 10.3 months and 18.4% improvement (HR = 0.84) from 8.2 to 9.7 months, respectively.

With an average accrual rate of 31.5 subjects per month and using a 2:1 treatment allocation ratio, a total of approximately 760 subjects (507 subjects in the cabozantinib arm and 253 subjects in the placebo arm) are required to observe the required number of events within the planned study duration (25 months accrual and approximately 38 months to observe the required deaths for OS).

**Open-Label Phase:** data for subjects who crossover from the placebo arm to receive cabozantinib, will be summarized separately and will not be included as part of the evaluation of either arm.

**Maintenance Phase:** data for subjects who enter the Maintenance Phase will not be entered in the clinical database. Data from the safety database will be summarized or listed separately.

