- Subjects randomized to the placebo arm will have the option to crossover to receive treatment with cabozantinib if they meet the eligibility criteria for crossover to cabozantinib after treatment with placebo.
- Subjects randomized to the cabozantinib arm who are still receiving study treatment, and subjects randomized to the placebo arm who are still receiving study treatment and do not crossover to cabozantinib, may continue on unblinded study treatment until a criterion for protocol-defined discontinuation has been met.
- Subjects randomized to the cabozantinib arm who are in the post-treatment period, and subjects randomized to the placebo arm who do not crossover to cabozantinib and are in the post-treatment period, will continue with post-treatment assessments as outlined in Table 12 of Appendix B.

If the study transitions to the Open-Label Phase, enrollment will be discontinued.

In the Open-Label Phase safety assessments will continue, efficacy and AFP assessments will be per standard of care; PK, biomarker, HRQOL, and health care resource utilization assessments will be discontinued.

See Section 5.3 and Appendix B for more details.

**Maintenance Phase:** When sufficient data have been collected to adequately evaluate all study endpoints, and upon site notification by the Sponsor, subjects remaining on study treatment will enter the study Maintenance Phase. Upon initiation of the Maintenance

Phase, the Sponsor considers the safety and efficacy profile of the drug within this study to have been sufficiently established for regulatory purposes.

In the Maintenance Phase subjects will continue to receive study treatment until a criterion for protocol-defined discontinuation has been met (protocol Section 3.6.1). Subjects are to undergo periodic safety assessments (including local laboratory tests) and tumor assessments; the nature and frequency of these assessments are to be performed per standard of care. It is the Investigator's responsibility to ensure that subject visits occur frequently enough and adequate assessments are performed to ensure subject safety.

See Section 5.4 and Appendix C for more details.

**Post-Treatment Period:** The final safety assessment will occur at the post-treatment follow-up visit 30 (+14) days after the date of the decision to discontinue treatment) unless a Grade 3/4 AE or an SAE is determined to be ongoing.

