## **TUMOR ASSESSMENTS**

---

Radiographic tumor assessments at screening will include CT or MRI of the chest, abdomen, and pelvis (CAP) and a technetium bone scan. If MRI is used for the CAP evaluation a noncontrast CT chest must be obtained unless prohibited by local regulations. The same imaging modalities used at screening will be used for subsequent tumor assessments.

CT/MRI assessments will be made at screening, 8 weeks after randomization, and every 8 weeks thereafter. Disease status will be determined at the local site (ie. Investigator and/or radiologist) using RECIST version 1.1.

CT/MRI of the chest/abdomen/pelvis should include a noncontrast study of at least the liver followed by contrast with triphasic CT imaging of the liver or liver MRI with gadolinium enhanced imaging. CT/MRI of the brain will be acquired at screening as clinically indicated (suspicion of brain metastasis). CT/MRI of the brain will be continued post-baseline only in subjects with documented brain metastases or as clinically indicated (suspicion of brain metastasis on study). MRI is the preferred method for brain imaging.

Whole body technetium bone scans will be performed within local standard of care guidelines and results provided in original DICOM format. All subjects will have a bone scan at screening. Follow up scans will be performed at 8 and 16 weeks after randomization, and then every 16 weeks for subjects with documented bone lesions at screening or as clinically indicated (suspicion of bone metastasis on study).

Radiographic assessments will continue on these schedules irrespective of whether study treatment is given, reduced, interrupted, or discontinued, until the later of 8 weeks after radiographic disease progression per RECIST 1.1 as determined by the investigator or the date of the decision to permanently discontinue study treatment (Appendix A). Detailed instructions for tumor imaging will be provided in a separate manual.

A blood sample for alpha-fetoprotein (AFP) assessment will be obtained by central laboratory every 8 weeks to correlate with each radiographic disease assessment visit.

If the study transitions to the Open-Label Phase or to the Maintenance Phase, tumor assessments will be done per standard of care; AFP will no longer be collected and analyzed by the central laboratory. AFP assessments may continue via local laboratory per standard of care.

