### **9.3.2 Objective Response Rate (ORR)**

The ORR is defined as the proportion of subjects experiencing a confirmed complete response (CR) or confirmed partial response (PR) per RECIST 1.1. The tumor response will be assessed by investigator.

Hypothesis testing will be performed using the Fisher's exact test at the 2-sided  $\alpha=0.01$  level of significance.

Point estimates of ORR, the difference in ORR between the two treatment arms, and associated confidence intervals will be provided. 95% CIs will be calculated using exact methods except for the difference in ORR between the two treatment arms which will use asymptotic confidence limits.

If sufficient responses are observed, additional supportive analyses will be conducted using appropriate methods to adjust for stratification factors.

The primary analysis of ORR will be performed for those subjects who have measurable disease at baseline within the ITT population. Subjects who do not have any post-randomization tumor assessments will be counted as non-responders.

The testing of ORR will occur only if the result of either an interim analysis or the final analysis of OS achieves statistical significance. If the p-value for the two-sided Fisher's exact test is less than 0.01 and the point estimate for ORR in the cabozantinib arm is higher than that in the placebo arm, the null hypothesis of no difference in ORR will be rejected and it will be inferred that ORR is superior in the cabozantinib arm compared with the placebo arm.

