### 7.2.2.3 Primary Analysis

Hypothesis testing for ORR will be performed using the Fisher's exact test at the 2-sided  $\alpha$ =0.01 level of significance. If a sufficient number of responders are observed, analysis using the Cochran-Mantel-Haenszel (CMH) method to adjust for stratification factors per IxRS may also be conducted. The testing of ORR will occur only if the result of either an interim analysis or the final analysis of OS achieves statistical significance. The primary analysis of ORR will include all subjects in the ITT population.

Point estimates of ORR for each treatment arm, the difference in ORR between the two treatment arms, and associated confidence intervals will be provided. The odds ratio and its confidence intervals will also be shown. The 95% CIs for the point estimate will be calculated using exact methods. The 95% CIs for the difference in ORR between the two treatment arms and for the odds ratio will be calculated by asymptotic methods.

If the p-value for the two-sided Fisher's exact test is less than 0.01 and the point estimate for ORR in the cabozantinib arm is higher than that in the placebo arm, the null hypothesis of no difference in ORR will be rejected and it will be inferred that ORR is superior in the cabozantinib arm compared with the placebo arm.

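### If OS crosses at an interim look, ORR is analysed with no minimum follow-up, so subjects randomised too recently to have a confirmed response count as non-responders and pull the estimate down

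*Protocol*

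**What the plan says.** **Trigger.** OS has "two interim analyses and a final analysis when 311, 466 and 621 deaths (ie, 50%, 75% and 100% information) have been observed respectively" (Protocol synopsis, Statistical Methods). Testing of PFS and ORR "will occur only if the result of either an interim analysis or the final analysis of OS achieves statistical significance". Protocol 9.8 and SAP 7.4 add that after an interim crossing the secondary analyses go ahead as planned. No interim ORR analysis is foreseen, so ORR is tested once.

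**Denominator.** SAP 7.2.2.3: "The primary analysis of ORR will include all subjects in the ITT population". Protocol 9.3.2 instead limits the primary ORR analysis to ITT subjects with measurable disease at baseline, and adds: "Subjects who do not have any post-randomization tumor assessments will be counted as non-responders".

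**Timing of response.** "CT/MRI assessments will be made at screening, 8 weeks after randomization, and every 8 weeks thereafter" (Protocol synopsis, Tumor Assessments). SAP 7.2.2.1 requires confirmation at a later visit at least 28 days after the response was first seen.

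**After a crossing.** The study may move to an Open-Label Phase at the sponsor's decision. "If the study transitions to the Open-Label Phase, enrollment will be discontinued", and tumor assessments then follow standard of care.

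I found no minimum follow-up for ORR, no stated ORR data cutoff and no planned ORR update in either document.

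**The concern.** Under the planning assumptions the first OS look comes while enrollment is still open. A subject randomised a few weeks earlier has had no scan, or only one, and cannot yet be a confirmed responder. Both ORR definitions keep that subject in the denominator as a failure; the protocol's measurable-disease restriction does not remove recent enrollees. ORR, the difference between arms and their confidence intervals would then reflect how recently subjects were enrolled as well as what the drug does. PFS does not share the problem, because such subjects are censored. This would be the only formally planned ORR result.

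**Working it through.** **Inputs.** Protocol synopsis and 9.9: "With an average accrual rate of 31.5 subjects per month and using a 2:1 treatment allocation ratio", 760 subjects, exponential OS, medians 8.2 and 10.8 months (HR 0.76), looks at 311, 466 and 621 deaths, "90% power for a 2-sided log-rank test with a 5% level of significance". Protocol 9.2.2: critical p-values 0.0031, 0.0183 and 0.044. Month = 30.4375 days (SAP 4). Assumed: uniform accrual, no dropout, ORR cut at the OS cutoff.

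**Reproducing the plan.**
- Events for 90% power: (1.960 + 1.282)² / [(2/9)·(ln 0.76)²] = 628, against 621 stated.
- Expected deaths at month t, with accrual rate r, accrual end T = 760/31.5 = 24.1 and a = min(t, T): Σ w·r·[a − (e^(−λ(t−a)) − e^(−λt))/λ], where w = 1/3 and 2/3, λ = ln 2/8.2 = 0.0845 and ln 2/10.8 = 0.0642. This reaches 621 at month 38.0; the plan says approximately 38.

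**First look.** At t = 20.8: placebo 10.5 × (20.8 − 9.79) = 115.6; cabozantinib 21 × (20.8 − 11.48) = 195.7; total 311. Randomised by then: 31.5 × 20.8 ≈ 655.

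| Time since randomization | Subjects | Share of 655 |
|---|---|---|
| under 8 weeks (no scan due) | 31.5 × 1.840 = 58 | 8.9% |
| under 12 weeks (scheduled first scan plus 28 days not reached) | 31.5 × 2.760 = 87 | 13.3% |
| under 16 weeks (second scheduled scan not reached) | 31.5 × 3.680 = 116 | 17.7% |
| under 24 weeks | 31.5 × 5.520 = 174 | 26.6% |
| under 32 weeks | 31.5 × 7.359 = 232 | 35.4% |

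With the 11.7-month median that the plan ties to the first-look boundary, the look falls at month 21.2 and the 12- and 16-week shares are 13.0% and 17.3%.

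**Relative ORR shortfall at the first look.** Each response is lost if its confirming scan lies beyond the cutoff. The timing scenarios are assumptions:
- all seen at week 8, confirmed at week 12: 13.3%
- all seen at week 8, confirmed at week 16: 17.7%
- 2/3 at week 8, 1/3 at week 16, confirmed at the next scan: 2/3 × 17.7 + 1/3 × 26.6 = 20.7%
- 50/30/20 over weeks 8/16/24, confirmed at the next scan: 0.5 × 17.7 + 0.3 × 26.6 + 0.2 × 35.4 = 23.9%

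Late responses are plausible: one of the three partial responses in the Phase 2 HCC cohort came after Week 12 (Protocol 1.3.3.3.2). A true ORR of 5%, the Phase 2 rate, would be reported as 5 × (1 − 0.133) = 4.3% down to 5 × (1 − 0.239) = 3.8%.

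**Second look and slower accrual** (cabozantinib median 10.8). SAP 2.4 says accrual is below 31.5 per month without giving a figure; 25, 22 and 20 are assumptions.

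| Accrual per month | Look 1: under 12 / 16 weeks | Look 2: under 12 / 16 weeks |
|---|---|---|
| 31.5 | 13.3% / 17.7% | 0% / 2.3% |
| 25 | 11.5% / 15.3% | 6.0% / 9.0% |
| 22 | 10.6% / 14.1% | 8.1% / 10.8% |
| 20 | 9.9% / 13.3% | 7.6% / 10.1% |

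At the final look the share is zero throughout.

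**How likely an early crossing is.** Simulating the three log-rank statistics at HR 0.76 with the stated critical values gives a 25% chance of first crossing at look 1, 42% at look 2 and 22% at the final look (total 89%; the plan states 90%).

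**Effect on the test.** Take 20 responders among 437 and 1 among 218 (655 in all): Fisher p = 0.0036. Removing the 31.5 × 117/30.4375 = 121 subjects with under 117 days leaves 534, or 356 and 178; with the same responders, p = 0.0035.

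**The case against.** The strongest reply is that the consequence is modest. A first-look crossing has about a one-in-four chance under the design effect. At planned accrual the second look is nearly clean and the final look entirely so. The shift is about one percentage point at a 5% response rate, inside the exact 95% interval of 2.8% to 7.0% for 20/437. It runs in the conservative direction, and the Fisher decision is essentially unchanged. All of this stands, and it limits the point to estimation.

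Four stronger readings are tempting, and the documents do not support them:
- *That 18% cannot have a confirmed response at the first look.* Confirmation is allowed from 28 days, and Protocol 5.6 has unscheduled imaging collected. On a scheduled first scan the strict figure is 13%; the 18% assumes confirmation at the next scheduled scan.
- *That ORR is a fifth too low.* This needs a response-time distribution that neither document gives. The supportable statement is a range.
- *That the estimate can never mature.* The Open-Label Phase is optional. Without it, 8-weekly scanning continues, and nothing bars a later descriptive update. What can be said is that no update is planned.
- *That the error rate is compromised.* If response timing is similar in both arms, both rates shrink by the same proportion and type I error is not inflated.

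It can also be said that no text ties the ORR cutoff to the interim OS cutoff. That is correct, but the silence is part of the problem: analysing ORR when OS crosses, on the data then in hand, is the natural reading.

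**Conclusion.** The point holds as one about estimation. Following the plan at an early OS crossing gives an ORR and arm difference biased toward zero: by about 13% to 24% in relative terms at the first look under planned accrual, across the assumed response timings. Slower accrual lowers the affected share at the first look (13% to 15% under 16 weeks at 20 to 25 per month) but carries the problem to the second (9% to 11%). These figures rest on uniform accrual, exponential survival at the design medians, no dropout, and ORR being cut at the OS cutoff. Because ORR is a formally tested secondary endpoint and no update is planned, the plan should deal with this before unblinding.

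**What to change.** In SAP 7.2.2.3 and Protocol 9.3.2:
1. State that the ORR data cutoff is the OS cutoff.
2. Reconcile the SAP's all-ITT set with the protocol's measurable-disease set, and keep the Fisher test at 0.01 on that agreed population.
3. Prespecify that, if OS crosses at an interim look, the ORRs, their difference and the confidence intervals are also reported for subjects in that population randomised at least 117 days before the cutoff (16 weeks plus the 5-day window), as the estimate to interpret.

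The restriction depends only on the randomization date, so the randomised comparison is preserved. It removes most of the bias, not all: under the 50/30/20 timing the residual shortfall is about 0.3 × (26.6 − 17.7)/82.3 + 0.2 × (35.4 − 17.7)/82.3 = 7.5%, so a true 5% is reported as 4.6% instead of 3.8%.

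The cost is one flag, one table and slightly wider intervals from about 120 fewer subjects at the first look. SAP 4.8 requires substantive changes to be documented before unblinding; a denominator chosen after OS has crossed would be post hoc.

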## LIST OF ABBREVIATIONS

Abbreviation or Term	Definition
AE	adverse event
AFP	alpha fetoprotein
AIDS	acquired immunodeficiency syndrome
ALT	alanine aminotransferase
ANC	absolute neutrophil count
AST	aspartate aminotransferase
AUC	area under the plasma drug concentration time curve
AUC 0-∞	AUC from the time of dosing to infinity
AUC 0-last	AUC from the time of dosing to the time of the last quantifiable concentration
β-HCG	β-human chorionic gonadotropin
BCLC	Barcelona Clinic Liver Cancer
BP	blood pressure
BSC	best supportive care
CAP	chest, abdomen, and pelvis
CFR	Code of Federal Regulations
CI	confidence interval
CL/F	oral clearance
CLIP	Cancer of the Liver Italian Program
CR	complete response
CRO	contract research organization
CT	computerized tomography
CTC	circulating tumor cells
CTCAE	Common Terminology Criteria for Adverse Events
CTP	closed testing procedure
CYP	cytochrome P450
DVT	deep vein thrombosis
(e)CRF	(electronic) case report form
EC	Ethics Committee
ECG	electrocardiogram
ED 50	dose required for 50% tumor growth inhibition
EGFR	epithelial growth factor receptor
EMA	European Medicines Agency
FBE	free base equivalent weight of cabozantinib
FDA	Food and Drug Administration
FFPE	formalin-fixed paraffin embedded
FXa	coagulation factor X

Abbreviation or Term	Definition
GCP	Good Clinical Practice
GI	gastrointestinal
HbA1c	hemoglobin A1c (glycosylated)
HBV/HCV	Hepatitis B virus/Hepatitis C virus
HCC	hepatocellular carcinoma
HGF	hepatocyte growth factor
HIV	human immunodeficiency virus
HLM	human liver microsomes
HR	hazard ratio
IC 50	concentration required for 50% target inhibition
ICF	informed consent form
ICH	International Conference on Harmonisation
IDMC	Independent Data Monitoring Committee
IRB	Institutional Review Board
ITT	intent to treat
IVC	intravenous contrast
IVR	interactive voice recognition
IWR	interactive web response
K iapp	apparent inhibition constant
LMWH	low molecular weight heparin
MedDRA	Medical Dictionary for Regulatory Activities
MET	hepatocyte growth factor receptor protein
MRI	magnetic resonance imaging
MTC	medullary thyroid cancer
MTD	maximum tolerated dose
NCCN	National Comprehensive Cancer Network
NSAID	nonsteroidal anti-inflammatory drug
NSCLC	non-small cell lung cancer
ONJ	osteonecrosis of the jaw
ORR	objective response rate
OS	overall survival
PE	pulmonary embolism
PFS	progression-free survival
PK	Pharmacokinetics
PPE	palmar-plantar erythrodysesthesia
PR	partial response
Qd	once daily
QT	time interval in ECG reading

Abbreviation or Term	Definition
QTcF	corrected QT interval by Fridericia
RCC	renal cell carcinoma
RECIST	Response Evaluation Criteria In Solid Tumors
RFA	radiofrequency ablation
ROW	rest of world
RPLS	reversible posterior leukoencephalopathy
RP2D	recommended Phase 2 dose
SAE	serious adverse event
SAP	Statistical Analysis Plan
SEM	standard error of measurement
SoD	sum of the diameters
SLD	sum of longest diameters
Tc	Technetium
TEAE	treatment-emergent adverse event
TIA	transient ischemic attack
$t_{1/2}$	half-life
TKI	tyrosine kinase inhibitor
$T_{max}$	time to maximum concentration
ULN	upper limit of normal
UPCR	urine protein:creatinine ratio
VEGF(R)	vascular endothelial growth factor (receptor)
V/F	oral volume of distribution (V/F)
VHL	von Hippel-Lindau gene
WBC	white blood cell
XL184	Exelixis code name for investigational product cabozantinib

